8.5 NEWS2

The NEWS2 has seven parameters which are scores from zero to three providing an overall score between zero and 20. The scores for each parameter can be found in the table below.

Score	3	2	1	0	1	2	3
Respiratory Rate	≤8		9-11	12-20		21-24	≥25
SaO₂	≤91	92-93	94-95	≥96			
Pulse Rate	≤40		41-50	51-90	91-110	111-130	≥131
Systolic BP	≤90	91-100	101-110	111-219			≥220
Temperature	≤35.0		35.1-36.0	36.1-38.0	38.1-39.0	≥39.1	
Neuro				Alert			Confusion, Voice, Pain, Unresponsive
Air or Oxygen		Oxygen (based on FiO ₂ >21%, or FiO ₂ >0 L/min)		Air			

Missing data: Any missing data will be imputed with the value zero, therefore classifying missing as normal. Low rates of missing data are expected for the physiological parameters. Sensitivity analysis will be considered if physiological variables have missing rates > 5%. The score will not be calculated if fewer than three of the parameters are available. The scale for patients with confirmed hypercapnic respiratory failure will not be used. For ROC analysis the raw score outlined above will be used. To calculate sensitivity and specificity at key cut-offs high risk will be defined as scoring at least 5, or scoring 3 points in any one of the above categories.

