7.1.2 Missing AVPU

For the multivariable analysis models AVPU will be used and GCS Total will be used to impute AVPU score where AVPU is not available. The following rules will be used:

- GCS 15 = A,
- GCS 9-14 = V,
- GCS 7-9 = P,
- GCS 3-6 = U.

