8.3 PMEWS

PMEWS uses six physiological parameters and patient parameters to calculate a score from zero to 19. The score is calculated by taking the score in the table below dependent on each of the six physiological parameters then adding points for two patient parameters after if they are positive.

Physiological:

Score	3	2	1	0	1	2	3
Respiratory Rate	≤8			9-18	19-25	26-29	≥30
SaO ₂	<89	90-93	94-96	>96			
Pulse Rate	≤40	41-50		51-100	101-110	111-129	≥130
Systolic BP	≤70	71-90	90-100	>100			
Temperature		≤35.0	35.1-36.0	36.1-37.9	38-38.9	≥39	
Neuro				Alert	Confused Agitated*	Voice	Pain Uncon

* confused/agitated will be defined based on GCS-V<4 or GCS total<15, or if confusion is ticked as a presenting feature

Patient:

- 1. Add 1 point if age>65
- 2. Add 1 point if either:
 - a. Patient lives alone / no fixed abode or
 - b. has a co-morbidity (respiratory, cardiac, renal, immunosuppressed, diabetes)
 - c. performance status is more than two suggesting limited activity can self-care, limited activity limited self-care, or bed/chair bound no self-care.

Missing data: If data is missing one or two variables then the normal score (zero) should be assumed. If more than three variables are missing the patient should be excluded. These rules effectively classify

missing data as normal. Low rates of missing data are expected for the physiological parameters and age. The remaining parameters only account for one point and therefore would be within the range of using the patient data. Sensitivity analysis will be considered if physiological variables have missing rates > 5%. If AVPU is missing and GCS is recorded, impute the following AVPU scores using GCS: 0 if GCS=15, 1 if GCS=12-14; 2 if GCS=9-11 and 3 if GCS<9.

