POPS is copyright (creative commons attribution non-commercial sharealike 4.0) [name] and [name] 2010 This is version 1.2 August 2015

An adjusted POPS will be scored based on the availability of data for our cohort.

- **Gut feeling** will not be scored.
- **Breathing** will be given a score of 2 if either severe respiratory distress or respiratory exhaustion is ticked, and a score of 0 otherwise
- Other will be given a score of 1 if any of premature, heart disease, asthma, diabetes, steroid therapy or other chronic lung disease is ticked, and 2 points if immunosuppression or active malignancy is ticked.

Any missing data will be assumed as normal. A score will not be calculated if fewer than three of the above are complete.

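### NEWS2 and POPS have no GCS rule for the consciousness item, so a patient with GCS below 15 and blank AVPU is scored as alert when the SAP is read as written

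*SAP*

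**What the plan says.** Section 7.1 sends missing data in the existing tools to the tool-specific rules in section 8. For NEWS2, section 8.5 says: "Any missing data will be imputed with the value zero, therefore classifying missing as normal". The NEWS2 Neuro row gives 0 for alert and 3 for "Confusion, Voice, Pain, Unresponsive". High risk is then defined as follows: "high risk will be defined as scoring at least 5, or scoring 3 points in any one of the above categories". No GCS rule is given.

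Section 8.7 (POPS) scores a row labelled AVPU. It lists three adjustments for the available data (gut feeling, breathing, other), none of which involves GCS. It ends with the same sentence as the WHO sections: "Any missing data will be assumed as normal".

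Other parts of the SAP do use GCS:

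- **CURB-65 (8.2):** confusion is positive on GCS or AVPU.
- **PMEWS (8.3):** "If AVPU is missing and GCS is recorded, impute the following AVPU scores using GCS".
- **Swine Flu item F (8.4):** positive if GCS is below 15 or AVPU is not alert.
- **WHO child rule (8.6.1):** positive if GCS is below 13 or AVPU is P or U.
- **Prediction models (7.1.2):** "For the multivariable analysis models AVPU will be used and GCS Total will be used to impute AVPU score". Appendix 1 and footnote a in section 6.3 say the same for the models.

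The WHO adult rule has no consciousness item. The altered-consciousness item in COAST is not tied to either field.

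**The concern.** The SAP foresees patients with a GCS but no AVPU, and handles them for the models and for PMEWS. The NEWS2 and POPS sections do not, and their missing-means-normal rules then fill the gap. The rule in 7.1.2 cannot simply be read across, because it is worded for the multivariable models.

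Recorded evidence of reduced consciousness is therefore discarded in two of the tools being compared and used in most of the others and in the new models. On NEWS2 this matters more than one lost item usually would, because a single 3 is enough for high risk. Affected patients with an adverse outcome can be counted as low risk, which lowers the reported sensitivity of that tool through data handling and not through the tool itself.

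**Working it through.** **1. Weight of the consciousness item, from the SAP's own tables.** NEWS2 has six items with a maximum of 3 and oxygen with a maximum of 2: 6 × 3 + 2 = 20. This matches the stated range, "providing an overall score between zero and 20". POPS without gut feeling has seven items with a maximum of 2: 7 × 2 = 14, matching the stated 0 to 14. Consciousness therefore carries up to 3 of 20 points on NEWS2 and up to 2 of 14 on POPS.

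**2. Score by GCS when AVPU is blank.** NEWS2 and POPS are shown as written, then with AVPU derived from GCS by the 7.1.2 mapping.

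| GCS | NEWS2 Neuro | POPS AVPU | PMEWS neuro | CURB-65 confusion | Swine Flu F |
|---|---|---|---|---|---|
| 15 | 0 → 0 | 0 → 0 | 0 | 0 | no |
| 12–14 | 0 → 3 | 0 → 1 | 1 | 1 | yes |
| 10–11 | 0 → 3 | 0 → 1 | 2 | 1 | yes |
| 9 | 0 → 3 | 0 → 1 or 2 | 2 | 1 | yes |
| 7–8 | 0 → 3 | 0 → 2 | 3 | 1 | yes |
| 3–6 | 0 → 3 | 0 → not defined | 3 | 1 | yes |

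GCS 9 is ambiguous on POPS because 7.1.2 assigns 9 to both V and P. GCS 3–6 maps to U, which the POPS chart does not score; it would be 2 if treated as the worst category.

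**3. When the classification changes.**

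- NEWS2, 5 or more: when the other items total 2, 3 or 4.
- NEWS2, 5 or more or any single 3: when the other items total 0 to 4 with no other 3.
- POPS, 5 or more: when the other items total 4 (Voice), or 3 or 4 (Pain).

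**4. Worked adult record.** GCS 10, AVPU blank, respiratory rate 20, SaO₂ 96 on air, pulse 95, systolic pressure 120, temperature 37.5. Only pulse scores (1). As written, NEWS2 = 1, low risk. With GCS used, NEWS2 = 1 + 3 = 4 with a 3 in one category, high risk.

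**5. Size for NEWS2 sensitivity.** The SAP gives none of the inputs, so all three are assumptions:

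loss = P(AVPU blank, GCS charted) × P(GCS < 15 given event) × P(otherwise low risk)

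This treats the three as independent and gives no credit for a ticked confusion box.

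| Blank AVPU, GCS charted | GCS < 15 among events | Otherwise low risk | Loss (percentage points) |
|---|---|---|---|
| 5% | 5% | 20% | 0.05 |
| 5% | 15% | 30% | 0.225, about 0.2 |
| 20% | 15% | 30% | 0.9 |
| 40% | 25% | 40% | 4.0 |

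The top row is the low end of the assumed ranges and the bottom row the high end. The second row fits best with the SAP's expectation of low missingness in physiological parameters. Over 200 events it is 0.00225 × 200 = 0.45 patients.

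**The case against.** **The NEWS2 row is not labelled AVPU.** It is called Neuro and includes confusion, which is not an AVPU level. Elsewhere (8.2, 8.3) the SAP defines confusion through GCS. On that reading a GCS of 10 makes the item available and the zero rule never applies. This stands in part: scoring the patient as alert is the natural reading of 8.5 but not the only one. But 8.5 does not define confusion, or say whether the ticked feature counts, as 8.3 does for PMEWS. Either reading needs to be written down. For POPS the row is labelled AVPU and the gap is plain.

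**Missingness is expected to be low, and there is a safeguard.** Section 8.5 says: "Sensitivity analysis will be considered if physiological variables have missing rates > 5" per cent. The expectation does make the likely effect small. The safeguard is only to be considered, names no GCS method, and is not given for POPS.

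**Inferences that the SAP does not support.**

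- A reader might infer that the error carries into Swine Flu criterion G, which uses NEWS2. It has no consequence there: GCS below 15 already makes item F positive, and one positive item is enough.
- A reader might infer that the error always works against NEWS2 and POPS, or biases the choice of comparator in section 6.5. The lost points can only lower sensitivity, but scoring zero in patients without an adverse outcome can raise specificity. The comparator is chosen by AUROC, and no AUROC effect has been shown.
- A reader might infer that every other tool uses GCS. The WHO adult rule and COAST are exceptions, as noted.

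**Conclusion.** The point holds as a scoring rule that, followed as written, gives a wrong score from data already collected. It is certain for POPS and the natural reading for NEWS2. The loss per affected patient is 3 points and the single-item flag on NEWS2 at any GCS from 3 to 14. On POPS it is 1 point at GCS 10–14 and 2 points at GCS 7–8.

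The effect on reported sensitivity is unknown, because the share with GCS only is not stated. It is about 0.2 percentage points for NEWS2 under the low-missingness assumptions above, and 0.05 to 4 points over the wider assumed ranges. The finding supports a correction to make the tools comparable. It does not support a claim that the ranking of tools, or any advantage of the new ones, is an artefact.

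**What to change.** **Section 8.5.** State that if AVPU is missing and GCS is recorded, a GCS below 15 scores 3 on the Neuro item. The 7.1.2 and PMEWS mappings agree that such a patient is not alert, so the choice between them does not matter here. State also whether the ticked confusion feature counts as confusion. Score 0 by default only if no consciousness field is recorded.

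**Section 8.7.** State that AVPU is derived from GCS with the 7.1.2 mapping when AVPU is missing. First reconcile the overlap at GCS 9 in 7.1.2, and state how U is scored on the POPS chart.

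**Leave the PMEWS mapping in 8.3 in place.** Lifting the restriction in 7.1.2 for all tools would collide with it: GCS 12–14 scores 1 under 8.3, but maps to Voice under 7.1.2, which is worth 2 on PMEWS.

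The cost is a few sentences and two small decisions (GCS 9 and U). Both GCS and AVPU are already collected. Reporting how many patients have GCS but no AVPU would settle the size.

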8.6 The WHO decision-making algorithm for hospitalisation with pneumonia

The WHO decision making algorithm for hospitalisation with pneumonia suggests an adult patient is admitted (score 1) if any of the following are present:

• respiratory rate >30/minute,

- oxygen saturation <90%,
- respiratory distress,
- age >60,
- any of the following comorbidities; hypertension, diabetes, cardiovascular disease, chronic respiratory disease, renal impairment immunosuppression

A patient will score 0 otherwise. Any missing data will be assumed as normal. A score will not be calculated if fewer than three of the above are complete.

8.6.1 WHO algorithm in children

The WHO decision-making algorithm for hospitalisation with pneumonia suggests a child is admitted (score 1) if any of the following are present:

- respiratory rate: >30/minute if over 5 years old; \ge 40/min if 1-5 years old; or \ge 50/min if <1year old
- oxygen saturation <90%
- respiratory distress, respiratory exhaustion or severe dehydration ticked
- AVPU is P or U, or GCS<13
- any of the following comorbidities are present; diabetes, cardiovascular disease, chronic respiratory disease, renal impairment, immunosuppression

A patient will score 0 otherwise. Any missing data will be assumed as normal. A score will not be calculated if fewer than three of the above are complete.

8.7 **POPS**

Paediatric Observation Priority Score (POPS) will be calculated for the child cohort only. The scoring chart is given below:

Paediatric Observation Priority Score (POPS) Chart

This chart is not a substitute for good clinical judgement and any concerns about the condition of a child should be brought to the attention of a senior nurse or doctor

Age	Score	2	1	0	1	2	Total	
Any	Sats	<90%	90-94%	>95%	90-94%	<90%	Score	Priority
Any	Breathing	Stridor	Audible grunt or wheeze	No distress	Mild or Moderate Recession	Severe Recession	0-1	
Any	AVPU	Pain	Voice	Alert	Voice	Pain		
Any	Gut Feeling	High level concern	Low level concern	Well	Low level concern	Child looks unwell	2-3	
Any	Other	Oncology Patient	Significant PMH*		Significant PMH*	Congenital heart disease	4-7	Immediate
							0.	review
	Pulse	<90	90 - 109	110 - 160	161 - 180	180+		
0-1	RR	<25	25 - 29	30 - 40	41 - 50	50+	Any c	hild scoring
	Temp	<35°	35 – 35.9°	36 - 37.5°	37.6 - 39°	39°+	abov	e 8 should
							he cor	sidered for
	Pulse	<90	90 - 99	100 - 150	151 - 170	170+	tranef	for to resus
1-2	RR	<20	20 - 24	25 - 35	36 - 50	50+	uansi	er to resus
	Temp	<35°	35 - 35.9°	36 - 38.4°	38.5 - 40°	40°+		
							*Signifi	cant PMH
	Pulse	<80	80 - 94	95 - 140	141 - 160	160+	include	s:
2-5	RR	<20	20 - 24	25 - 30	31 - 40	40+		
	Temp	<35°	35 - 35.9°	36 - 38.4°	38.5 - 40°	40°+	Ex-pre	emature
							Synar condit	ions
	Pulse	<70	70 - 79	80 - 120	121 - 150	150+	Cardia	ac problems
5-12	RR	<15	15 - 19	20 - 25	26 - 40	40+	Asthr	na l
	Temp	<35°	35 - 35.9°	36 - 38.4°	38.5 - 40°	40°+	Diabe	tes
			50.00		100 110		Long	term steroids
10.10	Pulse	<50	50 - 60	60 - 100	100 - 110	110+	 All oth 	er chronic
13-16		<12	12 - 14	15 - 20	20 - 25	25+	condit	ions
	Temp	<35°	35 - 35.9°	36 - 38.4°	38.5 - 40°	40°+		

POPS is copyright (creative commons attribution non-commercial sharealike 4.0) [name] and [name] 2010 This is version 1.2 August 2015

An adjusted POPS will be scored based on the availability of data for our cohort.

- **Gut feeling** will not be scored.
- **Breathing** will be given a score of 2 if either severe respiratory distress or respiratory exhaustion is ticked, and a score of 0 otherwise
- Other will be given a score of 1 if any of premature, heart disease, asthma, diabetes, steroid therapy or other chronic lung disease is ticked, and 2 points if immunosuppression or active malignancy is ticked.

Any missing data will be assumed as normal. A score will not be calculated if fewer than three of the above are complete.

8.8 COAST

COAST will be scored in children only using the 2018 COAST ED charts; there is a separate chart used to score infants (0-1years), preschool (1-4 years), schoolage (5-12 years) and teenage (13-18 years) which are not included in this SAP. COAST is scored by giving one point for each of

- Doctor/nurse/family concern
- abnormal heart rate for age

- abnormal respiratory rate for age
- abnormal SaO2
- mod/severe respiratory distress
- altered consciousness
- pain score

A modified COAST score will be calculated for children, to reflect the data we are collecting

- Excluding pain score
- Only recording severe respiratory distress
- Only recording score for parental concern (parental anxiety)

Hence, the COAST score is out of a possible 6 and will only be scored if at least 3 of the factors are available. If at least three of the factors are available the missing factors will be assumed normal (score 0).

Neme	No. of	6	Description	
Name	items	Score range	Description	Interpretation of score
CURB-65	5	0 - 5		0-1 = low risk, 2 = intermediate risk, 3-5 =
				high risk
PMEWS	8	0 - 19		0 – 2 = low risk, 3+ = high risk
Swine flu	7	N/A		Any one item is positive then should be
hospital				considered a risk
pathway				
NEWS2	7	0 - 20		0 – 4 low risk, any score of 3 on one or 5+
				high risk
WHO	5	0,1		0 = do not admit, 1 = admit
POPS	7	0-14		0-4 low risk 5+ high risk
COAST	6	0-6		0-2 low risk, 3+ high risk

8.9 Triage tool summary table

9 Implementation of the analysis plan

This SAP will be used as a work description for the statistician(s) involved in the study. All analyses will be performed by statisticians in the study team, under the supervision of the senior statistician, none of the investigators involved in the trial will perform any of the statistical analyses.

Due to the observational nature of the data, statisticians have export rights to the database and are able to query data in an ongoing manner. Any queries will be communicated to the data manager prior to database lock, and any changes to the database during this time will be documented. The database will be locked after an agreement between the statistician, data manager and study manager. It is expected that no data amendments should be required following database lock. However, if an amendment is required, the process is documented in CTRU SOP DM012.

10 Appendix 1 – Missing data imputation details

Variable	Deterministic imputation – imputing	Multiple imputation		
	based on 'normal'	What features are associated with this &		
		so used to predict? NB all will be		
		predicted using outcome also		
Model 1 – presenting character	ristics			
Demographics				
Age	No. Don't include patients that have this	No		
	missing			
Sex	No. Don't include patients that have this	No		
	missing			
Ethnicity	No. Conduct sensitivity analysis limited to	No		
	those with available ethnicity data.			
	Otherwise may have to remove from			
	model dependent on level of missing data.			
Current status				
Symptom duration	No	Yes: Age, presenting features,		
		comorbidities		
Number of current	Missing = no medications	Yes: Age, Medical history/complications.		
medications				
Presenting features	Absent/not ticked = no	N/a		
-Shorthess of breath -cough				
-fever	Although prevalence checks will be made			
-sore throat -headache	for presenting features, where the			
-confusion	prevalence is much lower than expected			
-rash -anosmia	we will assume that feature was not			
-abdominal pain	recorded across many sites and will			
-diarrhoea -vomiting	explore removing it from the model			

Lifestyle	Absent/not ticked = no	N/a
-Pregnant	Although prevalence sense checks will be	
-tobacco/vape user	conducted as above.	
Paediatric questions	Absent/not ticked = no	N/a
-routine vaccination	Although prevalence sense checks will be	
-taking feeds	conducted as above.	
-premature		
Performance status	Assume unrestricted normal activity	Yes: Age, medical history
known contact with Covid-19	Not ticked = no	N/a
case		
Severe respiratory distress	Not ticked = no	N/a
Respiratory exhaustion	Not ticked = no	N/a
Severe dehydration	Not ticked = no	N/a
Medical history		
Previous attendance	Not ticked = no	N/a
Current use of antibiotics	Not ticked = no	N/a
Medical History	Absent/not ticked = no, unless 'none' i.e.	Yes (for those with all including 'none'
-Heart disease	no medication is not ticked, if so assume	missing) age, number of current
-renal impairment -steroid therapy	missing.	medications
-asthma		
-diabetes		
-immunosuppression		
- other chronic lung disease		
-hypertension Physiology		
Central capillary refill		Yes: age, sex and physiology
Respiratory rate	Yes when categorised see section 6.3 for	Yes: age, sex and physiology
	dotails	res. age, sex and physiology
Dulas vata	uetans	"
	"	"
Temperature		
Systolic Blood Pressure		
SaO ₂	" 	"
SaO ₂ /FiO ₂ ratio	SaO2 assume normal (100), assume	Yes: age, comorbidities and other
	missing FiO2 = 21% and compute the from	physiology (respiratory rate, chronic lung,
	this	pulse, AVPU and BP).

	Could we impute FiO2 from age,			
	comorbidities and other physiology (or			
	just chronic lung disease and resp rate)?			
	Use of supplemental O2 will be			
	determined by respiratory rate and			
	chronic lung disease (and maybe pulse,			
	AVPU and BP).			
AVPU	Using GCS total – see 7.1.2, otherwise	Yes Using GCS deterministically, otherwise		
	assume A	using physiology		
Model 2 – including further tests				
Bloods				
Na	Yes, when categorised, see section 6.3 for	Yes: other bloods, age, sex, comorbidities		
	details	and physiology		
К	"	"		
Hb	"	"		
Platelets	"	"		
WCC	"	"		
Neutrophils	"	"		
Lymphocytes	"	"		
Lactate	"	"		
C-Reactive	"	"		
Urea	"	"		
Creatinine	"	"		
D-Dimer				
Troponin				
Other investigations				

"

Yes assume normal

Yes assume normal

CXR

ECG

11 References

- [1] Collins, G. S., Reitsma, J. B., Altman, D. G., & Moons, K. G. (2015). Transparent reporting of a multivariable prediction model for individual prognosis or diagnosis (TRIPOD): the TRIPOD statement. British Journal of Surgery, 102(3), 148-158.
- [2] Bossuyt, P. M., Cohen, J. F., Gatsonis, C. A., & Korevaar, D. A. (2016). STARD 2015: updated reporting guidelines for all diagnostic accuracy studies. Annals of translational medicine, 4(4).

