6.4 Development of predictive model and new triage tools

New triage methods will be developed by combining potential predictors of outcome using multivariable logistic regression with Least Absolute Shrinkage and Selection Operator (LASSO) to avoid overfitting [14].

Two new prediction models and subsequent triage scores will be developed: one based on clinical variables measured at initial assessment only (initial assessment model) and the other based on all clinical variables (including blood tests and x-rays) measured in the emergency department (full model). Both models will be built for adult and child populations separately (subject to the number of events in each population, if not enough events are observed in the child population we will not attempt to build prediction models).

Univariable screening of predictors will not be used as a basis for inclusion or exclusion into the predictive model as what matters is the association of predictors with outcome *after* adjustment for other predictors [15]. Using the LASSO begins with a full model of all potentially relevant predictors and simultaneously preforms predictor selection and penalisation during model development to avoid overfitting. This penalisation method essentially shrinks the estimated association between predictor and outcome towards the null, in order to reduce the variability of predictions when the model is used in new datasets.

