7.1 Missing data

Cases will be excluded from analysis if we are unable to ascertain if they had adverse outcome or not (i.e. they are missing follow up form). Cases will also be excluded from analysis if more than half of the variables used to develop a prediction model are not available. If particular sites have a large amount of missing data for key variables (for example age, respiratory rate) they will be excluded from analysis. The characteristics of cases with (≥20% missing) and without (<20% missing) missing data will be compared. A threshold of 20% has been chosen for comparison as we anticipate many cases to have some missing data due to the ED setting and the observational nature of this work.

It is likely that a proportion of data for most predictor variables (especially blood results) will be missing. A likely reason is that a measurement would not be made or test performed if it was expected to be normal. If a predictor variable has more than 50% data missing it will not be included in the multivariable predictive models.

Missing data will be handled in the following ways

- In the application of existing triage tools, the recommendations for handling missing data for each tool will be followed (see sections 8.2 to 8.5 for details).
- When investigating the univariate relationship between predictor and outcome (section 6.3) missing data will be treated as missing, or where appropriate treated as normal

- For building the prognostic models missing data will be handled in three ways and the results of these three scenarios will be compared, however the primary method will be multiple imputation
 - o Use multiple imputation to impute all missing predictor values
 - Assume missing predictor data is normal (when continuous variable are categorised, or when the outcome has a 'normal' option, for example CXR) or treat as missing if a continuous variable, or if no 'normal' category (see section 10 for details of which predictors will be imputed)
 - Treat all missing predictor data as missing

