7.1.1 Multiple imputation

Multiple imputation (MI) will be used to impute missing values for predictor variables in the development of the prognostic model only. At least 20 and ideally 50 multiple imputation data sets will be created using chained equations. Due to the large sample size for this study, it may be computationally intensive to have more than 20 MI data sets. The multiple imputation equation will include outcome and baseline variables with both missing and complete data (for example age, sex, presenting features) to make the missing at random assumption as plausible as possible. A list of which variable will be multiply imputed, together with the factors expected to be related and used in the imputation equations is given in section 10. The imputation model will be consistent with the prognostic model used for analysis, including the functional form of continuous variables.

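### Appendix 1's imputation lists omit many candidates of the LASSO models, contrary to section 7.1.1, and can bias the coefficients of the primary multiply imputed analysis

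*SAP*

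**What the plan says.** Section 7.1 compares three ways of handling missing predictors in the prognostic models, "however the primary method will be multiple imputation". On what goes into the imputation equations, section 7.1.1 says three things:

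- The equation contains the outcome and baseline variables, complete or not. Age, sex and presenting features are named as examples.
- "The imputation model will be consistent with the prognostic model used for analysis, including the functional form of continuous variables".
- A list of the variables to be imputed, together with "the factors expected to be related and used in the imputation equations is given in section 10".

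In Appendix 1 (section 10) each variable has its own short list, and a column note adds the outcome to all of them. Performance status has "Yes: Age, medical history". Central capillary refill, respiratory rate, pulse, temperature, systolic pressure and SaO2 have "Yes: age, sex and physiology".

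The analysis model is described in section 6.4: "Using the LASSO begins with a full model of all potentially relevant predictors". The candidates are those marked in the section 6.3 tables.

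**The concern.** An imputation model is consistent with an analysis model only if it carries the associations which the analysis model estimates. Lists that leave out co-predictors of the same regression do not. The outcome is included everywhere, so the familiar error of omitting it is not at issue here. The gap is among the predictors.

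This bears on the primary models. Section 7.1 expects missing values in most predictors and admits any predictor with up to 50% missing. Cross-validation and the bootstrap (7.3.4) address overfitting. They would not show a distortion built into every imputed data set by the same equations.

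**Working it through.** **Step 1. The lists against the candidate set.** The outcome is in every list. The last column gives candidates from section 6.3 that the list leaves out (not exhaustive).

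| Imputed variable | Appendix 1 list | Omitted candidates |
|---|---|---|
| Performance status | age, medical history | sex, presenting features, physiology |
| Number of medications | age, medical history | sex, presenting features, performance status, physiology |
| Medical history | age, number of medications | sex, presenting features, performance status, physiology |
| Most physiology | age, sex, physiology | medical history, performance status, presenting features |
| SaO2/FiO2 | age, comorbidities, other physiology | sex, performance status, presenting features |
| AVPU | GCS, otherwise physiology | age, sex, medical history, performance status, presenting features |
| Bloods | other bloods, age, sex, comorbidities, physiology | performance status, presenting features |

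Presenting features, which 7.1.1 names, appear only in the list for symptom duration. Sex, also named, is absent from the lists for performance status, symptom duration, number of medications, medical history, SaO2/FiO2 and AVPU. For performance status and physiology the omission is mutual: neither equation contains the other variable. The D-dimer, troponin, CXR and ECG cells are incomplete in the text at hand and are not used here.

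**Step 2. Why omission matters.** Let X be imputed from listed variables L and outcome Y, with co-predictor P left out. In the imputed rows Cov(X, P | L, Y) = 0. If a fraction f is missing completely at random, the residual covariance in the completed data is about (1 − f) times the true one: 0.9 times at f = 0.1, half at f = 0.5. The association of X with Y given L is preserved, including the part shared with P. The regression then sees less overlap between X and P than exists, and their coefficients shift.

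**Step 3. Size.** The SAP states no figure to reproduce. Its only usable input is the 50% cap, so everything else is assumed: 20,000 patients, about 9% events, a logistic model on age, medical history, X (a continuous stand-in for performance status, true coefficient 0.50) and P (a physiological variable, true coefficient 0.70). X is missing completely at random. There were 12 replicates and 3 normal-regression imputations. X was imputed from age, history and outcome, as in Appendix 1. Bias = mean coefficient / true coefficient − 1.

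| Residual correlation of X and P | X, 10% missing | X, 25% | X, 50% | P, 50% |
|---|---|---|---|---|
| 0 | 0.486 (−3%) | 0.488 (−2%) | 0.494 (−1%) | 0.697 (0%) |
| 0.15 | 0.515 (+3%) | 0.511 (+2%) | 0.546 (+9%) | 0.712 (+2%) |
| 0.3 | 0.522 (+4%) | 0.540 (+8%) | 0.579 (+16%) | 0.764 (+9%) |
| 0.5 | 0.527 (+5%) | 0.563 (+13%) | 0.621 (+24%) | 0.781 (+12%) |

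The Monte Carlo standard error for X is 0.007 to 0.016, or 1.4% to 3.2% of 0.50, so the 10% column is close to noise. With P added to the equation, X is 0.484 to 0.514 and P 0.683 to 0.706 in all settings.

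A second set of assumptions (20,000 patients, about 4% events, both log-odds ratios 0.588, same list) gives, relative to complete data at residual correlation 0.4: +14% and +15% for the two predictors at 50% missing, +5% and +9% at 30%, and about 3% at 10%. There is no inflation at correlation 0. Adding the co-predictor brings the estimates back to within about 4%.

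**Step 4. Prediction performance.** A simulation with a sparser list (age and outcome only) and 9% events changed the AUROC by at most 0.0004. The calibration slope fell by at most 0.02 at 5–10% missing, and by about 0.10 at 50% missing with correlation 0.5.

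**The case against.** The strongest reply is that 7.1.1 already contains the right rule. It asks for consistency with the prognostic model, no Appendix 1 list says that it is exclusive, and the column asks which features are associated with the variable. On that reading one sentence on precedence would do. But the column and 7.1.1 both say the listed factors are the ones used, and section 9 makes the SAP the statisticians' work description. An analyst could properly follow either instruction.

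Several limits on the size stand:

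- Sections 8.3 to 8.5 expect little missing physiology. Bloods, which 7.1 singles out as likely to be missing, have the broadest list.
- Section 6.4.1 keeps only one of a set of highly correlated factors, which limits the extreme correlations.
- Results are compared across three missing-data methods, one of which makes no use of these equations. A difference would be visible, though not its cause, and multiple imputation would remain primary.
- The simulations use unpenalised regression, and the SAP uses LASSO.

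A reader might also infer more than the document supports:

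- *That all physiology is imputed without comorbidities.* The SaO2/FiO2 list includes them.
- *That every omitted variable is a co-predictor in the final regression.* Under 6.4, only factors retained in the initial assessment model go forward to the full model, so presenting features missing from the bloods lists may not be in it.
- *That ethnicity was overlooked.* Appendix 1 gives it its own handling: a sensitivity analysis in patients with data, and possible removal from the model.
- *That the integer weights will be wrong.* This is not shown. In the worst setting of Step 3 the ratio of the two coefficients moves from 0.50/0.70 = 0.714 to 0.621/0.781 = 0.795, about 11%. Rounding and the planned clinical review may absorb that.

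**Conclusion.** The contradiction is in the text and depends on no simulation: equations restricted to the Appendix 1 lists cannot be consistent with a LASSO over the full candidate set. Followed as written, the lists can bias the multivariable coefficients and calibration of the primary analysis. It cannot be said that they will.

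For the imputed predictor, the bias ran from none without residual correlation, through about 5% or less at 10% missing, to roughly 15–25% at 50% missing with residual correlation 0.4–0.5. For the omitted co-predictor it was about 12–15% in that last setting. These figures rest on assumed coefficients, correlations and missing fractions, on data missing completely at random, and on positive correlations and effects. With other signs the direction may differ. The effect on discrimination was negligible where it was examined.

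One smaller inconsistency remains. Section 7.1 describes multiple imputation as covering every missing predictor value, while Appendix 1 marks ethnicity as not imputed. How a patient with missing ethnicity enters the primary imputed model is therefore not fixed.

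**What to change.** State in section 7.1.1 and at the head of Appendix 1 that each chained equation includes the outcome and all candidate predictors of the model being built (initial assessment or full), in the same functional form as in that model. Keep the Appendix 1 lists as minimum sets, and as the fallback if an equation does not converge. Report any variable for which the fallback was used.

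Reconcile section 7.1 with the ethnicity row by stating how patients with missing ethnicity enter the primary imputed model.

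The cost is SAP wording and computing time, which 7.1.1 already notes may limit the number of imputations. Larger equations may also fail to converge where categories are sparse, which is why the fallback should be written in.
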